1 BACKGROUND AND PRIOR EXPERIENCE

1.1 BACKGROUND

Non-contrast Cone Beam Breast CT (CBBCT) has received FDA PMA approval for diagnostic breast imaging. The CBBCT technique effectively removes overlap of breast structures, a confounding factor of the 2D mammogram study, and significantly improves the detectability of small breast tumors, independent of intravenous contrast agents, without vigorous breast compression. Of equal importance, results demonstrate that radiation exposure levels required for the CBBCT technique to detect small tumors (under 4 mm) and small calcifications (~0.2 mm) is within the same range of conventional diagnostic mammography [1].

The combination of detector resolution, small x-ray tube focal spot size, and imaging geometry enables the CBBCT system to achieve a reconstructed isotropic spatial resolution of (0.155 – 0.273 mm³). Isotropic high resolution allows reconstruction in any plane, without loss of detail, and a 3D volume reconstruction of superior spatial resolution. Isotropic high resolution is unique to the CBBCT method and to-date has not been feasible in other 3D breast imaging techniques. Current methods, primarily breast magnetic resonance imaging, are hindered by slice thicknesses typically 3-5 mm or more, which limits multi-planar reconstruction and limits the usefulness of 3D volumetric reconstruction. Therefore, CBBCT for breast-imaging may be able to more accurately identify small carcinomas (< 4 mm) and better delineate the extent of disease. CBBCT for breast-imaging provides the potential for a superior alternative to standard breast imaging techniques. [2] [3]

To further improve the detection of tumors and to distinguish cancer from benign lesions, the CBBCT is supplemented with the use of intravenous contrast agent. A Contrast Enhanced CBBCT (CE-CBBCT) typically requires a pre-contrast acquisition and a post-contrast acquisition.

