5.8 EXCLUSION CRITERIA

- Pregnancy
- Lactation
- Unknown pregnancy status AND
 - has refused pregnancy testing and
 - has refused to sign a pregnancy test waiver
- Women who are unable or unwilling to understand or to provide informed consent
- Women with physical limitations that may prohibit resting prone on the exam table, such as, but not limited to: frozen shoulder, recent heart surgery, pace maker.
- Women who are unable to tolerate study constraints.
- Women who have received radiation treatments to the thorax or breast area for malignant and nonmalignant conditions, such as (but not limited to):
 - Treatment for enlarged thymus gland as an infant
 - Irradiation for benign breast conditions, including breast inflammation after giving birth
 - Treatment for Hodgkin's disease

Clinical Trial Protocol			
Title:	Contrast-Enhanced Cone Beam Breast CT for Diagnostic Breast Imaging		
Internal #:	16-01		
IRB #:	RSRB00061893	NCT #:	NCT03354611
Revision:	3.5	Effective Date:	

- Women who have participated in a prior breast clinical trial that gave additional radiation dose, such as an additional mammogram.
- Women who have received large numbers of diagnostic x-ray examinations for monitoring of disease such as (but not limited to):
 - Tuberculosis
 - Severe scoliosis

Additional exclusion criteria due to contrast injection:

- Allergic to iodinated contrast material
- Previous non-ionic contrast reaction
- Any conditions below regardless of eGFR:
 - Renal Disease
 - Chronic Renal Insufficiency
 - Renal Transplant (or waiting for a transplant)
 - One Kidney or other birth defect
 - Polycystic Kidneys
 - Renal Tumor/Renal Cancer
 - Liver Failure
 - Cirrhosis
 - Liver Transplant (or waiting for liver transplant)
- Congestive heart failure
- Multiple myeloma
- Hyperthyroidism
- Pheochromocytoma
- Sickle Cell Disease
- Asthma requiring daily use of inhaler

Additional exclusion criteria due to machine limitations

- Patient's body weight is over the limit of the scanner table (440 lbs. or 200kg)

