6.1 CE-CBBCT PROCEDURE

The subjects will first have a pre-contrast CBBCT scan. Iodinated contrast will be injected intravenously, and then another CBBCT scans will be performed to capture the tumor vasculature enhancement. Features to look for are degree of enhancement pattern of the lesion as compared to surrounding pattern. Delay times and contrast volume/rate will be determined initially through previous CT studies then optimized through this CBBCT study. Each CBBCT scan takes 10 seconds and delivers a glandular dose similar to a diagnostic mammography exam. State board-certified and Mammography Quality Standards Act (MQSA) qualified mammographers will evaluate the CBBCT high resolution 3D images and compare them to the subjects' mammograms. If the subject had an MRI or ultrasound, then these would be compared as well. If the patient's diagnostic outcome is BIRADS 4 and above and has biopsy or surgery, pathology will provide final confirmation. If the patient's diagnostic outcome is BIRADS 1, 2, 3, follow up results will provide final confirmation.

Physicians familiar with contrast-enhanced multislice CT procedures will be available during the CE-CBBCT procedures and will advise on modifications.

Once all the projections are acquired, projections will then be used for volume reconstruction. Since a malignant tumor has many blood vessels, it will be enhanced in the post-contrast reconstructed image. The contrast enhancement of the malignant tumor will be quantified by CT number measurements. To explore dynamic contrast-enhanced vasculature patterns (wash-in, wash-out), we propose to select the scan at various delay times on different subjects with similar lesions to see if we can get preliminary data on this functional effect while keeping the dose to individual subjects low.

The radiographic technique will be 49 kVp, 8 ms/projection image, and 300 images per scan. The mA will be automatically selected by the CBBCT system from 50 to 160 mA, depending on size and density of the breast. This translates to a range of average glandular dose to the breast from ~4

Clinical Trial Protocol			
Title:	Contrast-Enhanced Cone Beam Breast CT for Diagnostic Breast Imaging		
Internal #:	16-01		
IRB #:	RSRB00061893	NCT #:	NCT03354611
Revision:	3.5	Effective Date:	

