Two MQSA qualified board-certified mammography radiologists will evaluate the CE-CBBCT study along with all prior imaging and histological results to determine the added value of CE-CBBCT. Initially, the radiologists will review the CE-CBBCT images and make independent diagnostic decisions blindly from MRI and ultrasound image results, if available. Next, they will compare the results of CE-CBBCT to diagnostic mammography, non-contrast CBBCT, MRI, and ultrasound images. Finally, they will compare their findings for each case to histological results, which are considered to be the quantitatively gold standard in diagnosis. The comparison will answer three questions:

1. Can the CE-CBBCT detect lesions that not detected by other modalities?
2. Can the CE-CBBCT better distinguish between benign and malignant masses?
3. Can the CE-CBBCT help show the extent of disease?

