9 ANALYSIS OF RESULTS

All data will be collected in a spreadsheet.

Contrast-enhanced CBBCT (CE-CBBCT) for breast imaging will be evaluated, tabulated, and analyzed in terms of lesion conspicuity and detail in comparison with the non-contrast CBBCT exam, mammogram, and contrast-enhanced breast MRI. We will evaluate wash in and wash out patterns and degree of enhancement of the lesion as compared to surrounding pattern.

Demographic and clinical characteristics of the study population will be described using mean and standard deviation for quantitative variables such as age, or percentage and percentiles for qualitative variables such gender, race, and cancer staging.

Reported adverse events will be tabulated according to its description, severity, and relationship to the specific imaging or clinical procedures. All patients will be included in the safety analysis.

Paired t-test (for quantitative measurements such as tumor size, time of wash in and wash out) or McNemar's test (for qualitative data such as type of mass, type of calcification) will be used for comparisons between the CE-CBBCT and other modalities.

Accuracy of diagnosis will be evaluated in terms of sensitivity and specificity by comparing the test results from each imaging modality to that of the biopsy (the gold standard). When sufficient data is available, comparisons between CE-CBBCT and the other modalities will then be conducted using McNemar's test.

No imputation will be used for missing data (i.e., only patients who have the specific data available will be included in a particular analysis.) Statistical analysis will be performed using SAS (SAS Institute, Cary, N.C., U.S.A.). All tests will be 2-sided with the confidence level set to 95%.

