For CE-CBBCT exam (one pre- and one post-contrast) the dose and associated risk increases linearly by the number of scans. The dose from a CE-CBBCT exam of one breast is ~8mGy to ~32mGy (+/- 20%) (depending on breast size and density). The amount of radiation exposure from one CE-CBBCT exam of one breast is equivalent to an effective whole-body dose of 1.2 mSv to 3.8 mSv, which is equivalent to approximately 4.6 months to 14.7 months of natural background radiation. This conversion is based on a breast tissue weighting factor of 0.15 per NRC 10CFR 20.1003 Definitions. In addition, this is meant to be a one-time study, not a periodic screening routine.

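### Section 6.3.3 specifies no standalone read of the pre-contrast scan, so the non-contrast CBBCT rating used in Section 9 is made with the enhancement already known

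*Protocol*

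**What the plan says.** Protocol Section 6.3.3 gives the whole review to one pair of readers: "Two MQSA qualified board-certified mammography radiologists will evaluate the CE-CBBCT study along with all prior imaging and histological results". The work is staged. In the first stage, "Initially, the radiologists will review the CE-CBBCT images and make independent diagnostic decisions blindly from MRI and ultrasound image results, if available". In the second, "Next, they will compare the results of CE-CBBCT to diagnostic mammography, non-contrast CBBCT, MRI, and ultrasound images". In the third, findings are set against histology.

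The composition of the exam is stated several times. Section 1.1: "A Contrast Enhanced CBBCT (CE-CBBCT) typically requires a pre-contrast acquisition and a post-contrast acquisition". Section 12.2: "For CE-CBBCT exam (one pre- and one post-contrast) the dose and associated risk increases linearly by the number of scans". Section 6.1: "The subjects will first have a pre-contrast CBBCT scan". Section 6.2.5 schedules one scan before contrast and one after it, and no other non-contrast CBBCT.

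Section 9 states that CE-CBBCT will be analysed "in terms of lesion conspicuity and detail in comparison with the non-contrast CBBCT exam", and also against the mammogram and contrast-enhanced MRI. It then plans paired t-tests or McNemar's test between CE-CBBCT and the remaining modalities. If the data suffice, McNemar's test is also to be applied to accuracy measured against biopsy.

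**The concern.** A contrast versus non-contrast comparison is informative about contrast only if the plain-scan rating shows what a reader would have seen without it. Under the stated order, the reader comes to rate the plain scan after deciding on an exam that includes the post-contrast images.

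The comparison matters to the protocol's argument. Section 1.1 presents contrast as a means of improving detection and separating cancer from benign lesions, and Section 1.2 says that contrast is needed to improve specificity. Section 1.2 also says that the second scan doubles the dose, and Section 14 notes that CBBCT is approved but that contrast use with it is not. The increment over the plain scan is what a reader will want from the Section 9 comparison, and the reading order mixes that increment with hindsight.

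**Working it through.** There is no stated figure to reproduce. The check sets the sections side by side.

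1. **Where the non-contrast images come from.** By Sections 1.1, 6.1, 6.2.5 and 12.2, the CE-CBBCT exam is a pre-contrast scan plus a post-contrast scan, and the pre-contrast scan is the only plain CBBCT scheduled. An earlier research scan is an unlikely source, because Section 5.8 excludes "Women who have participated in a prior breast clinical trial that gave additional radiation dose, such as an additional mammogram".

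2. **Whether a plain-scan result exists from elsewhere.** Section 8 lists physician reports for mammogram, ultrasound and breast MRI, where performed. It lists no report, and no separate image set, for non-contrast CBBCT. Mammography, ultrasound and MRI can thus have a result made outside this review, whereas non-contrast CBBCT has none listed.

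3. **What the readers know when they rate the plain scan.** The first stage masks readers to MRI and ultrasound only. The pre-contrast volume is not withheld, so it may be viewed beside the post-contrast volume at that stage, or taken up in the second stage. In both cases the enhancement is known when the plain scan is rated. Section 6.3.3 describes no prior read of the pre-contrast volume alone, no second set of readers, no washout and no randomised reading order.

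4. **Whether the analysis repairs this.** The paired t-test and McNemar's test account for two results coming from the same woman. They do not remove carry-over from one reading to the next.

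5. **Direction and size.** Conspicuity can be rated up because the reader now knows where to look, or rated down because the plain image looks poor beside the enhanced one. The same holds for accuracy, should non-contrast CBBCT be included there. For one reader and n cancers, let r be the cancers that the plain read gains through hindsight and d those that it loses through being marked down. The reported sensitivity difference (CE-CBBCT minus non-contrast) then equals the true difference plus (d − r)/n. The sign depends on whether d or r is larger, and the protocol gives neither. No magnitude can be derived.

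**The case against.** Four points on the other side deserve weight.

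- **The stakes are limited.** Sections 2 and 3 make case acquisition the only objective and endpoint. The hypothesis test belongs to a separate multi-reader study of CE-CBBCT plus two-view mammograms against diagnostic mammography (Synopsis and Section 1.2), where non-contrast CBBCT is not an arm. This stands. A reader might infer that the trial's main result or the pivotal comparison is compromised. The documents do not support that, since the Section 6.3.3 reads do not determine the endpoint and are not stated to feed the multi-reader study.

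- **Section 6.3.3 describes an open comparison.** Independence is claimed only for the first CE-CBBCT decision, and a side-by-side rating of conspicuity necessarily shows both image sets. This is fair, and a side-by-side rating may be reported if it is labelled as such. It does not supply an unaided plain-scan result.

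- **The link to accuracy is inferred.** Section 9 names non-contrast CBBCT only for conspicuity and detail. Its accuracy comparison is conditional on sufficient data and refers to the other modalities collectively. A reader might take a McNemar test of sensitivity between contrast and non-contrast as settled. It is possible, because Section 6.3.3 lists non-contrast CBBCT among the comparators, but the protocol does not commit to it.

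- **A separate read might be provided for elsewhere.** Section 7 refers to case report forms that are not shown, and Section 6.1 mentions an evaluation of the CBBCT images against mammograms without fixing its order. It would therefore be too strong to say that no unaided read can ever exist. But the reading order itself is set in Section 6.3.3. If a form or analysis plan calls for a plain-scan read before the enhanced one, that section still has to be changed to agree with it.

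**Conclusion.** The point holds in a limited form. Followed as written, Section 6.3.3 yields no unaided pre-contrast result. Any non-contrast rating of conspicuity and detail carried into Section 9 is then made with knowledge of the enhancement, as is any rating of detection or accuracy if non-contrast CBBCT counts among the other modalities.

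The conclusion rests on two readings of the protocol: that the pre-contrast scan is the non-contrast comparator, and that the forms not shown do not already require a locked plain-scan read. It is a weakness in a supporting comparison that is worth correcting because the correction is cheap.

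**What to change.** Amend Section 6.3.3 so that each radiologist:

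1. opens the pre-contrast volume alone, under the masking to MRI and ultrasound already stated and with mammography handled as it is now, and records and locks the ratings (conspicuity, detail, detection and diagnostic decision);
2. then opens the post-contrast volume and records the CE-CBBCT result under the same conditions, so that contrast is the only addition between the two steps;
3. then continues to the remaining comparisons and to histology as planned.

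In Section 9, name the locked read as the non-contrast CBBCT result and describe the comparison as the sequential added value of contrast. It should not be called a comparison of independent readings, because the CE-CBBCT decision now follows the same reader's plain-scan decision. True independence would need separate readers, or separate sessions with washout and randomised order, at greater cost.

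If the reading order is kept, the smaller remedy is to label the contrast versus non-contrast comparison in Section 9 as descriptive and unblinded.

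The main change costs protocol wording, one extra form section and a few more minutes per case. Readers, scans and dose stay the same. Its downside is the dependence of the CE-CBBCT decision on the preceding plain-scan decision, which should be stated when results are reported.

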7 DATA RECORDING

Information to be recorded on the participants includes:

- Subject age
- Date of Birth
- Height and weight
- Ethnic category
- Body habitus
- Measurement of breast
- Information to be recorded about imaging
 - Date of breast imaging studies
 - Date of CE-CBBCT imaging
- Pertinent clinical information, imaging data, interpretation data, and biopsy data will be recorded by hand through data sheets (CRF 1-13). All data will be subsequently entered into Excel spreadsheets to track results.

8 DATA COLLECTION

The following represents source documentation for data to be collected:

- Original mammogram OR reasonable quality copies of the subject's mammogram
- CE-CBBCT images
- Ultrasound images (if any)
- MR images (if any)
- CRF 1-6
- CRF 7-10 as appropriate
- Physicians Reports if performed for:

Clinical Trial Protocol			
Title:	Contrast-Enhanced Cone Beam Breast CT for Diagnostic Breast Imaging		
Internal #:	16-01		
IRB #:	RSRB00061893	NCT #:	NCT03354611
Revision:	3.5	Effective Date:	

- Mammogram
- Ultrasound
- Breast MRI
- Pathology Reports
- Definitive Surgery

9 ANALYSIS OF RESULTS

All data will be collected in a spreadsheet.

Contrast-enhanced CBBCT (CE-CBBCT) for breast imaging will be evaluated, tabulated, and analyzed in terms of lesion conspicuity and detail in comparison with the non-contrast CBBCT exam, mammogram, and contrast-enhanced breast MRI. We will evaluate wash in and wash out patterns and degree of enhancement of the lesion as compared to surrounding pattern.

Demographic and clinical characteristics of the study population will be described using mean and standard deviation for quantitative variables such as age, or percentage and percentiles for qualitative variables such gender, race, and cancer staging.

Reported adverse events will be tabulated according to its description, severity, and relationship to the specific imaging or clinical procedures. All patients will be included in the safety analysis.

Paired t-test (for quantitative measurements such as tumor size, time of wash in and wash out) or McNemar's test (for qualitative data such as type of mass, type of calcification) will be used for comparisons between the CE-CBBCT and other modalities.

Accuracy of diagnosis will be evaluated in terms of sensitivity and specificity by comparing the test results from each imaging modality to that of the biopsy (the gold standard). When sufficient data is available, comparisons between CE-CBBCT and the other modalities will then be conducted using McNemar's test.

No imputation will be used for missing data (i.e., only patients who have the specific data available will be included in a particular analysis.) Statistical analysis will be performed using SAS (SAS Institute, Cary, N.C., U.S.A.). All tests will be 2-sided with the confidence level set to 95%.

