1.2 PREVIOUS STUDIES

Approximately 600 CBBCT patients have been acquired in the United States under 5 IRB approved protocols including 81 BIRADS 4 & 5 patients who received CE-CBBCT scans. No adverse events were reported in these studies.

Based on clinical data from the previous studies, the CBBCT is comparable or exceeds breast tissue coverage as compared to mammography. Density is readily and reliably assessed. Breast anatomy is displayed exquisitely, showing vessels to <1 mm. Calcifications < 200µm are visualized with greater conspicuity, and distribution can be determined in 3D space. The CBBCT is equal or better than mammography for visualization of mass for conspicuity, border, and sharpness. The non-contrast CBBCT also assesses mass density accurately; but CT number alone may not improve specificity in the absence of IV contrast. Cancer size on CBBCT agrees with measurement from histopathology. Contrast enhancement is needed to further improve specificity. In the Contrast Enhanced CBBCT study, CE-CBBCT has high sensitivity, show greater extent of disease, and is able to detect new malignant lesions not previously detected on diagnostic work up or non-contrast CBBCT [1] [10] [11] [12] [13].

The CBBCT system has the feature to automatically determine the best mA required for the scan. This feature uses the two scout images at 0 and 90 degrees to estimate breast size, density, and automatically select the best mA to optimize image quality while keep the radiation dose as low as reasonably achievable. Analysis based on data from 220 patients has shown that the average mean glandular dose of one CBBCT scan and one diagnostic mammography exam is 10.6 mGy (standard

Clinical Trial Protocol			
Title:	Contrast-Enhanced Cone Beam Breast CT for Diagnostic Breast Imaging		
Internal #:	16-01		
IRB #:	RSRB00061893	NCT #:	NCT03354611
Revision:	3.5	Effective Date:	

deviation 3.89) and 9.57 mGy (standard deviation 5.16). The overall dose range is comparable and the dose values are less variable for the CBBCT [14].

Contrast-Enhanced CBBCT scan doubles the dose with a pre-contrast scan and a post-contrast scan. However, the total dose of a CE-CBBCT exam is 11.6mGy for a standard size, average dense breast. Given the tissue weighting factor of breast tissue is 0.12, a CE-CBBCT exam's effective dose is 1.39 mSv, which is about 5 months of nature background radiation dose in the United States [15].

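### Tumour size is compared between modalities only by a paired t-test, which cannot show which modality is closer to histological size; a reference-based size analysis would be a cheap improvement

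*Protocol*

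**What the plan says.** Section 9 (Analysis of Results) names the method for quantitative measurements as "Paired t-test (for quantitative measurements such as tumor size, time of wash in and wash out" and states that this test, or McNemar's test for qualitative data, "will be used for comparisons between the CE-CBBCT and other modalities". Histology is not a term in that comparison. The one analysis in Section 9 that uses a reference standard is sensitivity and specificity, obtained by "comparing the test results from each imaging modality to that of the biopsy (the gold standard"). That concerns diagnosis, not size.

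Section 6.3.3 (Review of the CE-CBBCT) describes a separate step. After reading the images, the two radiologists work case by case: "they will compare their findings for each case to histological results, which are considered to be the quantitatively gold standard in diagnosis". This comparison is to answer three questions, the third being "Can the CE-CBBCT help show the extent of disease". No size measure or size statistic is named for this step.

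Section 1.2 (Previous Studies) reports, as a result in favour of CBBCT, "Cancer size on CBBCT agrees with measurement from histopathology". It also lists a larger displayed extent of disease among the strengths of CE-CBBCT. Section 8 (Data Collection) lists "Pathology Reports" and definitive surgery reports as source documents, where performed.

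**The concern.** By the protocol's own account, a size measurement is good when it agrees with histopathology. The only statistic it names for size compares one imaging modality with another and does not use histology. A significant result says only that the mean sizes differ: CE-CBBCT could be larger because it depicts the tumour more fully or because it over-measures. A non-significant result says only that a mean difference was not detected, even if one modality is far more precise.

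The risk lies in interpretation. Section 1.2 already counts a larger displayed extent as an advantage, so a significantly larger mean size on CE-CBBCT invites a favourable reading that the test cannot support. A real gain in precision could equally pass unnoticed.

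**Working it through.** The protocol gives no expected size difference, SD or power for the size comparison, so there is no stated figure to reproduce. The check has an algebraic part, which needs no assumed values, and an illustration, which does.

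**Inputs from the protocol.** Paired t-test on tumour size between modalities, two-sided at 95% confidence (Section 9); at least 30 confirmed cancers (Section 2).

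**Assumed inputs.** Normal measurement errors, independent between modalities, with pathological size taken as the truth; biases of 0 to 4 mm; error SDs of 2 to 8 mm; all 30 cancers having a pathological size and a size on both modalities.

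**Algebra.** Let T be the true size, A = T + eA the size on CE-CBBCT and B = T + eB the size on the comparator. The paired difference is

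D = A − B = eA − eB.

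T has cancelled. The mean of D is bias(A) − bias(B), and this is all the t-test examines. Accuracy concerns the size of eA and of eB separately, which cannot be recovered from D.

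**Analytic check of one case.** Bias difference 4 mm, error SD 5 mm in each modality, n = 30:

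- SD(D) = √(5² + 5²) = 7.07 mm
- standard error = 7.07/√30 = 1.29 mm
- noncentrality = 4/1.29 = 3.10, which gives power of 85% on 29 degrees of freedom.

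The 4 mm can come from either modality; the calculation is the same.

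**Simulation, n = 30, 20,000 replicates, two-sided 5%.** The last column is a paired t-test on |A − T| − |B − T|, which needs the reference size.

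| Assumed truth | t-test on sizes rejects | Mean absolute error, CE-CBBCT / comparator (mm) | Test on absolute error rejects |
|---|---|---|---|
| Both unbiased, SD 3 and 6 | 5% | 2.4 / 4.8 | about 90% |
| CE-CBBCT over by 4, comparator unbiased, SD 5 | 85% | 5.2 / 4.0 | 26% |
| CE-CBBCT unbiased, comparator under by 4, SD 5 | 85% | 4.0 / 5.2 | 27% |
| CE-CBBCT over by 4, comparator under by 4, SD 5 | 100% | 5.2 / 5.2 | 5% |

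Rows two and three give the same mean difference (+4 mm), sign and rejection rate, although CE-CBBCT is the worse measure in one and the better in the other. Row one holds the 5% level although one modality has half the error of the other.

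**Other assumed values.** With a 3 mm bias difference and SD 3 mm, the t-test rejects in about 96% of trials whether the comparator under-measures by 3 mm, CE-CBBCT over-measures by 3 mm, or the two err by 1.5 mm in opposite directions. With both unbiased and SDs of 2 and 8 mm it rejects in about 5%. The same pattern appears with 20 and with 68 cancers.

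**Precision of a reference-based analysis.** With n = 30 and SD 5 mm, the 95% confidence interval for one modality's mean bias is ± 2.045 × 5/√30 = ± 1.9 mm.

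**The case against.** A reader might infer that the protocol uses the wrong test for its third question, on extent of disease. The documents do not support that. Section 9 assigns the t-test to comparisons between modalities and nowhere says that it settles extent or accuracy. Section 6.3.3 gives that question its own route, in which "they will compare their findings for each case to histological results". Nor are tumour size and extent shown to be the same thing; Section 1.2 mentions them separately. For the question whether mean sizes differ, the paired t-test is valid. In the table it does its job: it rejects when the means differ and holds 5% when they do not. What goes wrong would be the reader's inference, not the test. All of this stands.

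It can also be said that an agreement statistic is a detail for the statistical analysis plan, which is not shown. That carries part of the way: the missing statistic in Section 6.3.3 is not by itself a fault. But Section 9 does fix a method for size, and that method leaves out the reference that the protocol itself calls the gold standard.

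Three practical objections also stand. The biases and SDs are assumed, and the scenarios were chosen to show the contrast. Ultrasound and MR images are collected only if they exist, and pathology and surgery reports only if performed, so the paired sample may be smaller than 30. No section states that pathological size is recorded as a data item.

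**Conclusion.** The point holds as a modest improvement to a secondary analysis. The named size test cannot show which modality is closer to histological size. This follows from the algebra and does not depend on the assumed values. The percentages do depend on them and only illustrate how far the test result and the ranking by accuracy can part.

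It is not an error affecting the study's main aim. The primary objective and endpoint (Sections 2 and 3) concern acquiring cases, and the sample-size rationale (Section 4) rests on the area under the ROC curve in a separate reader study. No sample size or success criterion depends on tumour size.

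**What to change.** In Section 9, for cancers with a surgical pathology size:

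1. Report each modality's difference from pathological size: mean bias with 95% confidence interval, and 95% limits of agreement.
2. Compare absolute errors between CE-CBBCT and each other modality within patient, by a paired analysis.
3. Label the between-modality paired t-test on size as descriptive.
4. Refer to this analysis from the histology comparison in Section 6.3.3, which has no size statistic.

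No extra patients or procedures are needed, but it is more than a change of wording. Pathological size must be abstracted from the pathology or surgery reports, with a data field and a rule on which specimen supplies it. The analysis covers only women with a pathological size and a size on both modalities. With about 30 cancers the absolute-error test is weak (26 to 27% power for the assumed 4 mm bias and 5 mm SD), so bias and limits of agreement should lead, and a non-significant comparison of absolute errors should not be read as equal accuracy.
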